2.8.2.2.3. Duration of Response

The duration of response will be estimated for the FAS population. Duration of response is defined as the number of days from the first response date to the first relapse date (first relapse date – first response date + 1). The first response date is the first date of platelet count and LDH that a response is achieved. Relapse is defined as having a platelet count greater than 50% decrease from the maximum platelet count and a LDH greater than 1.5 times the upper limit of normal. Relapse will be evaluated using the platelet count and the LDH collected within 1 week. Duration of response will be censored at the last platelet or LDH collection date if relapse does not occur during the study. Kaplan-Meier analysis of the duration of response will be performed for the patients who achieve a response by dose for the FAS population. Median duration of response will be presented with 95% CI.

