[Khosla 2017]. Plasma therapy is thought to have no utility in this patient population [Khosla 2017, Rosenthal 2016]. Patients who do not respond to modification of their immunosuppression have a poor prognosis. Adult mortality has been reported to be as high as 100% (4 out of 4 patients, all of whom died within 69 days from diagnosis) [Worel 2007]. In a larger and more recent series, only 17% of adult patients (4 out of 24) who underwent immunosuppression modification and received treatment with plasmapheresis, defibratide, or rituximab survived 1 year [Bohl 2017]. Eculizumab has been reported to treat HSCT-TMA effectively with a 90% response rate when used off-label in 1 adult study; however, there was a high rate of infection-related mortality following eculizumab treatment [Bohl 2017]. These data demonstrate that HSCT-TMA is a life-threatening condition and, with the lack of effective treatment options, represents a significant unmet medical need.

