7.3.2. Secondary Endpoints

The secondary endpoints are to evaluate the following in patients with HSCT-TMA treated with OMS721:

- Duration of response, defined as the number of days from the first response date to the first relapse date

CONFIDENTIAL

No use, disclosure or reproduction outside of Omeros without prior written authorization

- 100-day survival, from the date of TMA diagnosis
- Overall survival, from the date of TMA diagnosis
- Freedom from platelet transfusion defined as no platelet transfusions for at least 4 weeks following the last platelet transfusion except for patients who died within 4 weeks of the last platelet transfusion (only evaluated in patients who had platelet transfusions in the 2 weeks prior to or on the first OMS721 dose date)
- Freedom from RBC transfusion defined as no RBC transfusions for at least 4 weeks following the last RBC transfusion except for patients who died within 4 weeks of the last RBC transfusion (only evaluated in patients who had RBC transfusions in the 2 weeks prior to or on the first OMS721 dose date)
- Change from baseline in platelet count (post baseline platelet counts without platelet transfusions 2 days before and on the day of the platelet count collection will be used) over time using central laboratory values
- Change from baseline in LDH over time using central laboratory values
- Change from baseline in haptoglobin over time using central laboratory values
- Change from baseline in Hgb (post baseline Hgb without RBC and whole blood transfusions 6 days before and on the day of the Hgb collection will be used) over time using central laboratory values
- Change from baseline in creatinine over time using central laboratory values
- The PK of multiple-dose administration of OMS721 (this will be assessed in patients with HSCT-TMA as well as patients with aHUS and TTP)
- The PD of multiple-dose administration of OMS721 (this will be assessed in patients with HSCT-TMA as well as patients with aHUS and TTP)
- The immunogenicity of multiple-dose administration of OMS721 (this will be assessed in patients with HSCT-TMA as well as patients with aHUS and TTP)

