19.5. Laboratory Measure Schedule

As available, local laboratory measures of platelet count, Hgb, white blood cell count, absolute neutrophil count, LDH, haptoglobin, creatinine, bilirubin, AST, ALT, alkaline phosphatase, and schistocytes will be collected according to the following schedule:

Pre-TMA period:

- Once immediately prior to conditioning
- On Day -1 or 0 prior to transplant (the measure closest to the transplant). (Day 0 is the day of transplant)
- On Days +2, +4, +6, +8, +10, +14, +21, +28 following transplant and weekly thereafter until 28 days prior to the diagnosis of TMA

TMA period:

- Daily from 28 days prior to the diagnosis of TMA to the later of 12 weeks following the diagnosis of TMA or 4 weeks following resolution of TMA

Post-TMA period:

- Once weekly following the TMA period for 4 weeks, then once every 2 weeks for 4 weeks, and then once monthly \pm 3 days until up to 2 years following the first dose of OMS721

Platelet count should be recorded immediately before and after each platelet transfusion.

Hemoglobin levels should be recorded immediately before and after each RBC transfusion.

Abbreviations: ALT = alanine aminotransferase; AST = aspartate aminotransferase; Hgb = hemoglobin; LDH = lactate dehydrogenase; RBC = red blood cell; TMA = TMA = thrombotic microangiopathy.

CONFIDENTIAL

No use, disclosure or reproduction outside of Omeros without prior written authorization

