aHUS = atypical hemolytic uremic syndrome; HSCT-TMA = hematopoietic stem cell transplant-associated thrombotic microangiopathy; TTP = thrombotic thrombocytopenic purpura

For patients with HSCT-TMA enrolled under Amendment [REDACTED] or under earlier versions of this protocol, additional data will be collected. Notification and consent of patients (or legal representatives for deceased patients) for this additional data collection will be performed as needed according to local rules and regulations.

These additional data are outlined in Protocol Amendment [REDACTED]. These data will include supplemental data on patient demographics and baseline conditions, donor characteristics, the transplant procedure, concomitant medications, TMA-related laboratory measures, transfusions, transplant complications, and outcomes. Details of these data are provided in Appendix 1 of the protocol amendment. These data will be derived from medical records from the time of transplant conditioning through the last available patient contact with the site or 2 years (104 weeks) after the first OMS721 dose, whichever is earlier. These data were requested by regulatory authorities because patients who have undergone HSCT typically have complicated post-transplant courses and these additional data will allow for better understanding of OMS721 response and outcomes. As of Amendment 11, enrollment in the study has been completed, and the additional data will be collected until a predetermined data cutoff date for those patients who have not reached 2 years after first OMS721 dose.

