2.8.2.2.2. Overall Survival

Overall survival will be calculated from the date of HSCT-TMA diagnosis. For the patients who are alive, their overall survival will be censored at the last known date of alive in the database. The method for handling a partially missing date of death is presented in Section 2.7.

Overall survival will be analyzed using Kaplan-Meier method by dose for the FAS population. Median overall survival and its 95% CI will be estimated by dose.

In addition, a competing risks analysis for overall survival will be performed. The cumulative incidence function of each pre-specified causes of death (GVHD, graft failure, infections, progression of underlying disease, HSCT-TMA, and others) will be estimated by nonparametric maximum likelihood method. The estimated cumulative incidence functions and their 95% CI will be displayed graphically.

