2.8.2.2.5. Additional Analysis of Secondary Efficacy Endpoints

The analyses of the secondary efficacy endpoints specified in the previous sections (Section 2.8.2.2.1, 2.8.2.2.2, and Section 2.8.2.2.4) will be performed separately for the responders and non-responders for the FAS population.

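### Duration of response counts only laboratory relapse and censors responders who die, so no planned output shows time alive and in response

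*SAP*

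**What the plan says.** Protocol 7.3.2 lists "Duration of response, defined as the number of days from the first response date to the first relapse date". SAP 2.8.2.2.3 and Protocol 13.2.5.2 supply the rule. Relapse is a platelet fall of more than 50% from the maximum together with LDH above 1.5 times ULN. On timing, "Relapse will be evaluated using the platelet count and the LDH collected within 1 week". For everyone else, "Duration of response will be censored at the last platelet or LDH collection date if relapse does not occur during the study". A Kaplan-Meier analysis in responders, by dose, then gives a median with a 95% confidence interval.

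Death is handled elsewhere. Overall survival runs from HSCT-TMA diagnosis. SAP 2.8.2.2.2 adds a competing-risks analysis: "The cumulative incidence function of each pre-specified causes of death (GVHD, graft failure, infections, progression of underlying disease, HSCT-TMA, and others") will be estimated. SAP 2.8.2.2.5 says that the analyses of 100-day survival, overall survival and the other secondary endpoints "will be performed separately for the responders and non-responders for the FAS population". Section 2.8.2.2.3 is not in that list.

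**The concern.** Death is not named in the duration-of-response rule, but the rule settles how it is treated. Relapse is the only event and every responder without relapse is censored, so a responder who dies in response leaves the risk set at the last laboratory date. The curve is then read as if that patient could still have relapsed later, at the same rate as those who remain.

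Deaths are to be expected in this disease. Protocol 5.1.2.3 cites a series in which "only 17% of adult patients (4 out of 24) who underwent immunosuppression modification and received treatment with plasmapheresis, defibratide, or rituximab survived 1 year". Those patients were not given OMS721 and were not selected as responders, so the figure shows that death is common in HSCT-TMA and supplies no rate for this analysis.

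The interim report is meant to enable a submission for drug approval (Protocol 13.2.10, SAP 2.8.5). A reader who sees a long median duration of response may take it as time alive and in response. It could equally reflect deaths removed by censoring.

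**Working it through.** **Is there an output that combines relapse with death?**

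| Planned output | Starts at | Relapse an event? | Death an event? |
|---|---|---|---|
| Duration of response (SAP 2.8.2.2.3) | first response | yes | no, censored |
| Overall and 100-day survival, all patients and responders (2.8.2.2.1, 2.8.2.2.2, 2.8.2.2.5) | TMA diagnosis | no | yes |
| Competing risks (2.8.2.2.1, 2.8.2.2.2) | TMA diagnosis | no | yes, by cause |

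None does in the visible text. The redacted block before SAP 2.8.4 is 2.8.3, which SAP 3.3 assigns to pharmacokinetics, pharmacodynamics and immunogenicity.

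**Inputs.** The plan states no figure for duration of response. Its sample-size sections use 28 HSCT-TMA patients and a 50% response rate, which gives 14 responders. The Clopper-Pearson interval for 14/28 is 30.65% to 69.35%, matching the stated 30.6% to 69.4%. Relapse and death rates in responders are not given, so those below are assumptions: a relapse-only median m of 365 or 180 days, one-year survival after response S of 90%, 70% or 50%, and constant, independent hazards.

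**Formulas.**
- Relapse hazard: hr = ln 2 / m. Death hazard: hd = -ln(S) / 365.
- Median with death censored: ln 2 / hr = m, whatever the death rate.
- Median with relapse or death as the event: ln 2 / (hr + hd).
- Probability of death before relapse within one year: hd / (hr + hd) x [1 - exp(-365(hr + hd))].
- One-year cumulative incidence of relapse: the same expression with hr in the numerator.

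**Example, m = 365, S = 70%.** hr = 0.6931/365 = 0.001899 and hd = 0.3567/365 = 0.000977 per day. The sum is 0.002876, so the median is 0.6931/0.002876 = 241 days. Death before relapse within a year is 0.3398 x (1 - 0.5 x 0.7) = 22.1%, and 14 x 0.221 = 3.1 responders.

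| Assumed one-year survival | 90% | 70% | 50% |
|---|---|---|---|
| Median, relapse or death (relapse-only 365 days) | 317 | 241 | 183 |
| Median, relapse or death (relapse-only 180 days) | 167 | 144 | 121 |
| Death before relapse within one year, m = 365 | 7.3% | 22.1% | 37.5% |
| The same, out of 14 responders | 1.0 | 3.1 | 5.3 |
| One-year relapse from 1 minus Kaplan-Meier, m = 365 | 50.0% | 50.0% | 50.0% |
| One-year cumulative incidence of relapse, death competing | 47.7% | 42.9% | 37.5% |
| Alive and relapse-free at one year (0.5 x S) | 45% | 35% | 25% |

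**Direction in small samples.** I simulated 10,000 trials of 14 responders with m = 365, the last laboratory date 0 to 30 days before death or cutoff, and follow-up to day 698 (728 days less an assumed 30 to response). The planned median was longer than the relapse-or-death median in about 64%, 95% and 99% of trials, and equal in the rest. A median that was not reached counts as longest. Equality arises when deaths fall late: relapses at days 50, 80, 100 and 120, one death at day 400 and two event-free patients give 120 days under either rule.

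**The case against.** Relapse-only duration is a legitimate quantity, it is openly defined, and survival is reported beside it, separately for responders. That number of responder deaths caps the number censored by death. With about 28 patients, the planned individual platelet and LDH plots and the narratives would let a careful reader trace cases by hand. The magnitudes are assumed, and they assume the independence that is itself in doubt. All of this stands. It limits the point to a labelling and supplementary-analysis matter, but it does not supply a summary of time alive and in response.

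Several stronger readings are tempting, and the documents do not support them:
- **The plan leaves the handling of deaths undefined.** It does not: the stated rule censors them without naming them.
- **Censoring at the last value of either test runs past the point where relapse could be assessed.** Relapse needs both criteria, so one platelet count that has not halved, or one LDH at or below 1.5 times ULN, rules it out on that date. Moving censoring back to the last paired date would discard valid relapse-free follow-up.
- **Long laboratory gaps before death distort the result.** They could, and could even reverse the direction. But Protocol 19.5 plans local values, as available, "Daily from 28 days prior to the diagnosis of TMA to the later of 12 weeks following the diagnosis of TMA" or 4 weeks after its resolution, then weekly, two-weekly and monthly. Collection runs to the last contact or "2 years (104 weeks) after the first OMS721 dose, whichever is earlier". Gaps of many months are not what the plan foresees.
- **The 17% survival figure measures the bias here.** It comes from a different population.

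**Conclusion.** The point holds as a gap in a secondary endpoint. The planned median answers how long until laboratory relapse if death did not occur, and it does so without bias only if death is independent of relapse. HSCT-TMA is a listed cause of death, so responders who die may be those nearest to relapse. In that case the estimate is too long even for its own target.

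The primary response analysis, with its 15% lower-bound criterion, is untouched. The size is unknown. Under the assumed hazards a 365-day median would become 317, 241 or 183 days at 90%, 70% or 50% one-year responder survival. If few responders die without relapse, or they die late, the two medians may coincide. A reader should not infer that the reported duration will be overstated by any particular amount, nor that the plan hides deaths.

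**What to change.** In SAP 2.8.2.2.3:
1. Keep the current analysis, label it as time to relapse with deaths censored, and report the number of responders censored by death.
2. Add a Kaplan-Meier analysis from the first response date with relapse or death from any cause as the event.
3. Report the cumulative incidence of relapse with death as a competing event.

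No new data are needed, because dates of death are already collected (Protocol 19.4, Table 2). Protocol 13.2 requires an amendment only when a principal feature changes and has the SAP finalised before interim database lock, so these additions can be made in the SAP by then. The cost is wording and a few extra outputs. The downside is that the relapse-or-death duration will probably be shorter than the relapse-only one and, with few responders, imprecise.

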13.2.5.2. Analysis of Secondary Efficacy Endpoints

The 100-day survival status will be determined as a binary variable. A patient achieves a 100-day survival if the overall survival from the date of HSCT-TMA diagnosis of the patient is ≥ 100 days. If the 100-day survival status of a patient is unknown (i.e., censored before 100 days), this patient will be considered to have died prior to 100 days. The 100-day survival rate will be estimated with exact 95% CI by dose for the FAS population.

Overall survival will be calculated from the date of TMA diagnosis. Overall survival will be analyzed using Kaplan-Meier method by dose for the FAS population. Median overall survival and its 95% CI will be estimated by dose.

The duration of response will be estimated for the FAS population. Duration of response is defined as the number of days from the first response date to the first relapse date (first relapse date – first response date + 1). The first response date is the first date that platelet count and LDH response is achieved. Relapse is defined as having a platelet count greater than 50% decrease from the maximum platelet count and an LDH greater than 1.5 times the ULN. Relapse will be evaluated using the platelet count and the LDH collected within 1 week. Duration of response will be censored at the last platelet or LDH collection date if relapse does not occur during the study. Kaplan-Meier analysis of the duration of response will be performed for the patients who achieve a response by dose for the FAS population. Median duration of response will be presented with 95% CI.

Binary secondary efficacy endpoints will be summarized with exact 95% CI by dose for the FAS population. Non-responder imputation will be used to handle missing data.

CONFIDENTIAL

No use, disclosure or reproduction outside of Omeros without prior written authorization

In addition, efficacy laboratory values of platelet count, LDH, creatinine, hemoglobin, and haptoglobin will be plotted over time for the HSCT-TMA patients.

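### Duration of response is censored at a platelet or LDH date that is not tied to the last time relapse could be assessed, and the text does not say which of the two dates applies

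*SAP*

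**What the plan says.** The event needs two laboratory findings together, with LDH judged against its upper limit of normal (SAP 2.8.2.2.3): "Relapse is defined as having a platelet count greater than 50% decrease from the maximum platelet count and a LDH greater than 1.5 times". The two values must also be close in time: "Relapse will be evaluated using the platelet count and the LDH collected within 1 week".

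The censoring rule names one test or the other: "Duration of response will be censored at the last platelet or LDH collection date if relapse does not occur during the study". Protocol 13.2.5.2 carries the same rule. Neither document says whether the later or the earlier of the two dates is meant, or requires a paired value at the censoring date. SAP 2.7 (missing data) does not address it.

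The analysis is descriptive: "Kaplan-Meier analysis of the duration of response will be performed for the patients who achieve a response by dose for the FAS population", with a median and 95% CI.

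On data collection, platelets and LDH are both drawn at every Cohort 5 treatment and follow-up visit, the last on Day 92 (Protocol 19.3). Beyond that there are local chart values up to 2 years after first dose, under Protocol 19.5, in a list that opens: "As available, local laboratory measures of platelet count, Hgb, white blood cell count, absolute neutrophil count, LDH, haptoglobin, creatinine, bilirubin, AST, ALT, alkaline phosphatase". In the post-TMA period the interval is "Once weekly following the TMA period for 4 weeks, then once every 2 weeks for 4 weeks, and then once monthly", within 3 days either way.

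**The concern.** In a Kaplan-Meier analysis a patient should leave the risk set when the event can no longer be observed. Here that is the last date with an evaluable platelet/LDH pair. If the rule is read as the later of the two last dates, a patient whose LDH is no longer recorded, but whose platelet counts continue, stays in the risk set although relapse cannot be declared under the plan's own definition. That time adds to the denominator and can contribute no event, so the curve is held up.

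There is some reason to think LDH is the test more likely to drop out. Platelet count is part of the hematology panel, while LDH is not in the chemistry panel listed in Protocol 12.1.1 and is named separately in the visit procedures. Protocol 19.5 also asks for platelet counts around each platelet transfusion and has no such trigger for LDH.

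Duration of response is the first secondary endpoint listed in SAP 2.1. The interim report is intended for a marketing submission, and only the responders among about 28 patients enter the curve. A censoring rule with two readings that can give different medians should be settled before the data are seen.

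**Working it through.** **No stated figure to reproduce.** The documents give no expected median, event count or LDH completeness for this endpoint. What follows shows direction and conditional size only.

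**Step 1. How far apart can the two dates be?**

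- Both tests collected to schedule: each falls within 3 days of the monthly date, so the two last dates differ by at most 3 + 3 = 6 days. They always form a pair within 1 week.
- LDH missing after the last scheduled visit: that visit is Day 92, and 104 weeks after first dose is 728 days, i.e. Day 729. The outer limit is 729 − 92 = 637 days, about 21 months. This is a bound, not an estimate.

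**Step 2. Bias under the later-date reading.** Assumptions, none from the documents: exponential time to relapse with true median 240 days; platelet counts to day 700 after response in everyone; LDH ending at a time U, uniform on 30 to 180 days after response, in a fraction f of responders, unrelated to relapse risk.

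Let S(t) = 2^(−t/240) and λ = ln 2 / 240 = 0.002888 per day. A patient who loses LDH can have no recorded event after U but is kept to day 700. For t between 180 and 700 days the curve therefore estimates

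S*(t) = (1 − f)·S(t) + f·E[S(U)],

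where E[S(U)] = (e^(−30λ) − e^(−180λ)) / (150λ) = (0.9170 − 0.5946) / 0.4332 = 0.744.

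Setting S*(t) = 0.5 gives a median of 240 × log2[(1 − f) / (0.5 − 0.744f)]. The 12-month value uses S(365) = 0.348.

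| Share losing LDH (f) | Median, later-date rule | Relapse-free at 12 months |
|---|---|---|
| 0 (truth) | 240 days | 35% |
| 5% | 249 days | 37% |
| 10% | 259 days | 39% |
| 25% | 302 days | 45% |
| 50% | 472 days | 55% |

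Simulation with 400,000 responders agrees: 250, 260, 303 and 470 days.

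**Step 3. The other reading, and last-pair censoring.** In this model the earlier of the two last dates is also the last evaluable pair. Censoring there, in the same simulation, gave medians of 241 days (rounded) in all four scenarios and about 35% at 12 months, so there is no bias.

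**Step 4. Different inputs.** With a true median of 12 months, platelet follow-up of 6 to 23 months and LDH stopping at month 3, simulation of 200,000 responders gave a later-date median of 16.6 months when 25% lose LDH, and not reached when 50% do. Last-pair censoring gave 12.0 and 12.1 months. With a gap of only about 6 days, as in complete collection, the later-date median was 12.2 against 12.0 months.

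**Step 5. Scale against sampling error.** For an assumed 15 responders, all followed past the median, the approximate standard error of a 240-day median is √(0.25/15) / (0.5λ) = 0.1291 / 0.001444 ≈ 89 days. A shift of 9 to 20 days (5% to 10% loss) is small beside this; 62 days (25%) is not negligible, and 232 days (50%) exceeds it.

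**The case against.** Several points on the other side stand.

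- **The wording does not fix the later date.** A reader might infer that months of undetectable relapse are built into the rule. The text does not support that: it is silent on which date applies, and the earlier date removes the bias in the scenarios above.
- **Divergence is possible, not documented.** Platelets and LDH share one schedule, and the as-available qualifier covers both. Nothing shows LDH stopping while platelet counts continue. The loss fractions used above have no source.
- **The endpoint is descriptive.** The efficacy criterion, a lower confidence bound above 15%, uses the response rate alone. Individual platelet and LDH plots are already planned (SAP 2.8.2.1), and the by-dose estimates will be imprecise in any case: SAP Table 1 lists only 4 HSCT-TMA patients at 370 mg.

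A reader might also infer that the clock starts too early, because a responder must meet a clinical criterion as well, while Protocol 13.2.5.2 says: "The first response date is the first date that platelet count and LDH response is achieved". This does not hold as an error. The start is openly defined, and running from a laboratory start to a laboratory relapse is coherent. Moving the start to the clinical criterion would need a rule for patients whose laboratory relapse comes first.

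What none of this removes is that the censoring date is undefined when the two dates differ, and that one natural reading is biased in the drug's favor.

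**Conclusion.** The concern holds as a specification gap with a conditional bias. The censoring date is ambiguous and not tied to the last date on which relapse could be assessed; nothing elsewhere in the documents corrects this. Under the later-date reading any bias is upward. It is about 9 days on a 240-day median at 5% LDH loss and 62 days at 25%, and it nearly doubles the median at 50%. These figures rest on the assumed relapse distribution, follow-up and pattern of LDH loss. The bias is negligible with complete collection or with the earlier date, and the actual size cannot be computed from the documents. Because this is a descriptive secondary endpoint, it is a should-fix: it does not affect the primary efficacy conclusion.

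**What to change.** In SAP 2.8.2.2.3 and Protocol 13.2.5.2, define the censoring date for responders without relapse as the last date on which a platelet count and an LDH were collected within 1 week of each other and did not meet the relapse definition. List for each responder the last platelet, last LDH and last paired dates. Run the later-date rule as a sensitivity analysis, so that the effect of any LDH loss is visible.

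Leave the start of the clock as it is. At most, label the endpoint duration of laboratory response.

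Two limits remain. Last-pair censoring assumes that LDH stops for reasons unrelated to relapse risk. It also does not deal with long gaps between pairs, where a transient relapse could be missed; if such gaps are expected, a maximum allowed gap should be set as well.

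The cost is one sentence in each document, one listing and minor programming. The reported duration may be shorter. Since Protocol 13.2 has the SAP finalized before the interim database lock, the change belongs before that point.
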